## **2. Methods**

### **Ethical Statement**

This study was reviewed and approved by the University of Pittsburgh's Internal Review Board. Informed consent was obtained from each participant. Participation in this project was completely voluntary for each individual subject. A nurse caregiver referred eligible patients on the unit to the principal investigator so as to prevent cold-calling. A random identifier was assigned to each participant to maintain confidentiality of recorded data.

### *2.1 Sample*

This study took place on the pulmonary step-down and transplant unit at a 1,600-bed academic medical facility in Southwestern Pennsylvania. Recruitment occurred after the nurse clinician in the pulmonary stepdown unit spoke with the patient and asked if they were comfortable discussing the study with the principal investigator (PI).

Inclusion criteria were adult patients 18 years of age and older with an existing diagnosis of either CF or COPD. The BDI-II survey was administered following a waiver to written consent and only patients with a score of  $>/= 14$  or mild depression symptoms were invited to participate. This minimum score was determined in order to be high enough to allow visible changes in depression symptoms following a seven day intervention. Demographics including diagnosis, education level, ethnicity, and age were recorded for each participant (Table 1).

Exclusion criteria included patients who had pre-existing ophthalmological conditions or photosensitivity due to the use of a bright light; migraines because the bright light could be a trigger; those receiving high dose steroids for transplant rejection due to potential for mood altering qualities; those receiving certain antibiotics that increased light sensitivity; those with bipolar disorder because light therapy may trigger mania; and admissions anticipated to span less than 48 hours because this would not be a long enough span for therapy to produce a visible effect on depressive symptoms. Children were excluded because only adult CF and COPD subjects are admitted to this hospital and unit. This study only consisted of one admission period for the inpatient. If the patient were to be readmitted, potential for bias from previous exposure existed; therefore, re-enrollment was not offered.

The initial target number of patients for this study was 30. With the primary interest being in feasibility and acceptability of this intervention, this study will assist in providing support for a larger-scaled study; therefore, a sample size of 30 is appropriate for these purposes. No power analysis was performed for this study.

### *2.2 Study Design*

This was a quasi-experimental, pre- and post- intervention, single group study. No control group was utilized for comparison. A single bright light lamp was assigned to each individual patient throughout the duration of the intervention.

## 2.3 Intervention

Procedures following consent began with placing a bright light therapy lamp in the participant's room and reviewing verbal instructions on what the subject should anticipate. Verilux HappyLight ® Luxe UV Free LED Therapy Lamp by Verilux was utilized for the purposes of this study. This is a 10,000 lux bright light therapy lamp which is a level of intensity comparable to being outdoors on a sunny but not overly bright day (Sloane, Figueiro, & Cohen, 2008).

Since participants with a history of bipolar mood disorder were excluded from this study, the 15-item "Mood Disorder Questionnaire" was administered manually from a printed paper survey during the pre-screening process to determine history of bipolar disorder symptomatology since this was not able to be determined solely based on medical chart review (Hirschfield, 2006). Basic demographic data including age, disease diagnosis, ethnicity, and education level was manually collected from each participant via a checklist completed by the PI (Table 1). At this time, a random identifying code was assigned to the participant for confidentiality. Bright light therapy began the morning following enrollment. The lamp was placed in a position approximately 16-24 inches from the subject's face by the principal investigator initially. Proper positioning of the lamp was included in bedside nurse education in order to ensure that it was placed correctly before being turned on each morning. A small reference sheet and disposable measuring tape was attached to each lamp to ensure continued proper use and distance from the patient. A preliminary 10-minute session of bright light therapy (BLT) was initiated following consent in order to ensure no acute reactions or sensitivities were experienced from the light. The brightness level was set at 10,000 lux. If the participant experienced sensitivity or adverse effects during this pretest time, which may have included eyestrain, headache, nausea, or irritability, therapy began at 2,500 lux the following day and gradually increased by 2,500 lux per day as tolerated by the patient. The PI was responsible for adjusting this setting in these instances. Color temperature was set to warm white (3,500K), medium white (4,250k), or daylight (5,000k) for the duration of the study depending on the participant's preference during pretesting. The participant was able to request that this be changed during the study when the PI would be present for routine monitoring. The PI also provided contact information to the participant and nursing staff so that she could be reached if needed. These settings were automatically saved when the lamp was turned off making it easy to maintain the same settings for seven days of therapy. The lamp stayed in the subject's room until the seven-day goal was completed or the patient was discharged or transferred. The bedside registered nurse turned on the lamp and set the timer upon entering the room in the morning when the patient would awaken. The automatic timer on the lamp turned off therapy after 30 minutes. The bedside nurse would initial a log documenting the day and time therapy was initiated and whether it was initiated on that day. The PI was responsible for routinely monitoring participants and following up on whether there were disruptions in therapies during each session (this was not the bedside nurse's responsibility). Disruptions may have included the patient self-discontinuing therapy for that day or leaving the

unit for testing, procedures, or hemodialysis. This information was recorded on the compliance log. The completion of this log was included in education regarding BLT provided to the bedside nursing staff by the PI.

The subject was responsible for and educated about how to turn off the lamp in the instance that he or she felt therapy should be disrupted during the 30-minute therapy period. This procedure did not differ on weekends or holidays since this took place in a 24-hour hospital facility. If the participant was discharged prior to completing the repeat Beck Depression Inventory II, he or she would be contacted via phone to verbally administer the inventory as included in the consent form.

When the bright light lamps were not in use, they were properly cleaned with purple top PDI wipes per the unit's infection control representative and stored in a pre-designated locked cabinet on the pulmonary stepdown unit.

#### *2.4 Measurements*

Depressive symptoms were obtained subjectively before and after the seven-day allotted intervention period utilizing the 21-item BDI-II scoring system (Beck, 1996). This scoring system considers a total score of 0-13 as minimal, 14-19 as mild depressive symptoms, 20-28 as moderate, and 29-63 as severe. The BDI-II is most often reported to have a Cronbach's Alpha coefficient averaging 0.9 and is shown to be highly reliable with the ability to provide differentiation between depressed versus non-depressed subjects (Wang & Gorenstein, 2013).

Compliance data was measured via a log posted on the participant's room door. This log was completed daily by the assigned bedside nurse and included the data, whether therapy was initiated (Y/N), what time it was initiated, and whether therapy was interrupted (Y/N). Reason for interruption could be added as a comment on the log, but there was no designated area in which to write it. These logs were collected by the principal investigator following completion of the intervention.

#### *2.5 Statistics*

Normality of pre- and post-intervention BDI-II scores was tested using the Shapiro-Wilk test. Given data normality, a paired student t-test was used to assess the primary outcome data. The secondary outcome of daily compliance data with the seven-day length intervention was tested utilizing a Chi-Square test. Final data was recorded as standard deviation with a mean with a two-tailed 0.05 significance value.

### **3. Results**

#### *3.1 Patient Characteristics*

Four participants were successfully enrolled in this study. Due to potential candidates who met one or more of the exclusion criteria, intensive care unit transfers, and those being transferred to alternative units after becoming COVID-19 positive, only four participants successfully completed the pre- and post- BDI-II scoring.

Twenty additional potential participants were screened and considered for enrollment in this study but met various exclusion criteria. These exclusion criteria included anticipated disposition in less than 48 hours (n=8), pre-existing ophthalmological conditions (n=2), did not meet initial depression inventory score minimum of 14 or greater (n=1), had a history of migraines (n=2), were receiving pulse dose steroids (n=1), and those who expressed general disinterest in participating in the intervention (6) (Table 3). Among these patients, 15 were diagnosed with CF and five were diagnosed with COPD.

Among the four who were successfully enrolled and completed the intervention three were diagnosed with CF and one was diagnosed with COPD. Ages ranged from 36 to 70 years old, with an average of  $56.25 \pm 20.25$  years. All participants were of Caucasian race. Total admission lengths spanned from 14 to 55 days among participants with the average being 31.25 days.

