## Tables

Table 1. Demographics

Number of participants	4
Diagnosis	
CF (%)	3 (75)
COPD (%)	1 (25)
Ethnicity	
Caucasian (%)	4 (100)

Age (mean in years)	$56.25 \pm 20.25$
Education Level	
High School (%)	2 (50)
College (%)	2 (50)

Table 2. Pre- and Post- BDI-II Scores

\*this figure will need color in order to see which color indicates pre- versus post-

Table 3. Reasons for Participant Exclusion

[figure not shown]

Table 4 & 5. BDI-II Analysis (Primary Outcome)

Paired Samples Statistics					
	Mean	N	Std. Deviation	Std. Error Mean	
Pair 1	Pre-BLT BDI-II	24.75	4	8.995	4.498
	Post-BLT BDI-II	16.00	4	5.944	2.972

Paired Samples Test								
Paired Differences								
	Mean	Std. Deviation	Std. Error Mean	95% Confidence Interval of the Difference				
Pair 1	Pre-BLT BDI-II - Post-BLT BDI-II	8.750	10.563	5.282	-8.059	25.559	1.657	3 .196

Table 6. Daily Compliance Analysis (Secondary Outcome)

Chi-Square Tests			
	Value	df	Asymptotic Significance (2-sided)
Pearson Chi-Square	12.000 a	9	.213
Likelihood Ratio	11.090	9	.270
Linear-by-Linear Association	.998	1	.318
N of Valid Cases	4		

a. 16 cells (100.0%) have expected count less than 5. The minimum expected count is .25.

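### Does the age summary of 56.25 ± 20.25 years, which cannot be a mean ± SD for four people aged 36 to 70, call for a change?

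*Combined protocol and SAP*

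**What the plan says.** Section 3.1 (Patient Characteristics) reports that "Four participants were successfully enrolled in this study". It then says "Ages ranged from 36 to 70 years old, with an average of" 56.25 ± 20.25 years. Table 1 repeats 56.25 ± 20.25 in a row whose label begins "Age (mean in years" and does not mention a spread. Neither place defines the ± term.

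The only statement on reporting format is in section 2.5 (Statistics): "Final data was recorded as standard deviation with a mean". That section otherwise deals with the tests of BDI-II scores and compliance and does not mention demographics.

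**The concern.** Given section 2.5, the natural reading of the age entry is mean ± SD. On that reading the sentence contradicts itself, because four values confined to a 34-year span cannot have a sample SD above 20. The same figure stands in the text and in the table, so a fault in reading the PDF is unlikely.

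Two things could be at stake. The description of a very small sample would be wrong in one of its few baseline entries. And an impossible baseline statistic raises the question of whether the outcome figures were handled with the same lack of care.

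**Working it through.** **Inputs.** n = 4, minimum 36, maximum 70, mean 56.25 and ± value 20.25 (section 3.1; mean and ± value also in Table 1). BDI-II figures are from Tables 4 and 5.

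**Is the mean possible?** Yes. The ages sum to 4 × 56.25 = 225. Taking out 36 and 70 leaves 119 for the two middle participants. In whole years between 36 and 70, 11 pairs give 119.

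**SD with the stated mean.**
- Smallest: 36, 59, 60, 70. The squared deviations are 410.06 + 7.56 + 14.06 + 189.06 = 620.75, and √(620.75/3) = 14.38.
- Largest: 36, 49, 70, 70. The squared deviations are 410.06 + 52.56 + 189.06 + 189.06 = 840.75 (from unrounded terms), and √(840.75/3) = 16.74.
- So 20.25 is too large by 20.25/16.74 = 1.21 to 20.25/14.38 = 1.41, that is 21% to 41%.

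**SD with any mean.** The maximum has two people at each end: 36, 36, 70, 70. Each deviation is 17, and √(4 × 289/3) = 34/√3 = 19.63. The printed value is 3% above this.

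**Allowing for rounding of ages.**
- Under one convention, either rounding or truncation, the true range is at most 35. The any-mean limit becomes 35/√3 = 20.21, only 0.04 below 20.25.
- With the stated mean the limit is 17.61 under truncation (36, 47, 71, 71) and 17.29 under rounding (35.5, 48.5, 70.5, 70.5).
- The bound with the stated mean is therefore the stronger argument.

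**Other readings of ±, over the 11 whole-year sets.**

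| Reading | Possible values |
|---|---|
| Population SD | 12.46 to 14.50 |
| Standard error | 7.19 to 8.37 |
| 1.96 × standard error | 14.1 to 16.4 |
| 95% t half-width (3.182 × SE) | 22.89 to 26.64 |
| 2 × SD | 28.8 to 33.5 |

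None of these contains 20.25.

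**Exact match.** 56.25 − 36 = 20.25. The distance to the oldest participant is 70 − 56.25 = 13.75, so the value would not be a symmetric spread: 56.25 + 20.25 = 76.5 lies above the stated maximum.

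**Does the fault reach the outcome data?** The printed BDI-II figures agree with one another:
- Mean difference: 24.75 − 16.00 = 8.75.
- Standard errors: 8.995/2 = 4.498, 5.944/2 = 2.972 and 10.563/2 = 5.282.
- Test: t = 8.750/5.282 = 1.657 on 3 df, two-sided p = 0.196.
- 95% interval: 8.75 ± 3.182 × 5.282 = 8.75 ± 16.81, that is −8.06 to 25.56.

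All match the tables.

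**Where age is used.** Section 2.1 requires only age 18 or over and states that no power analysis was done. Age does not appear in the paired t-test (section 3.2) or in the compliance analysis (section 3.3).

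**The case for a change.** The best case for acting is that the figure is demonstrably not what section 2.5 leads the reader to expect. It appears twice, and four source ages and two edits would put it right. With so few participants the age row is a main part of the description of who was studied, and anyone taking a baseline SD from Table 1 would take an impossible one. All of that stands as a reason to tidy the entry if the report is reissued.

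It does not make the point one about the plan. A reader of section 3.1 has the mean, minimum and maximum of four ages in one sentence, and these fit together. A corrected SD would add little to them and would alter no analysis or conclusion.

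From the opposite direction, it can be said that the ± term is never called an SD where it is printed, and that the one sentence supporting that reading is loosely worded and concerns outcome data. That is fair up to a point. What is shown is that the term is undefined and cannot be an SD. A miscalculated SD is not shown, and the match with mean minus minimum suggests a cause without proving it.

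**Conclusion.** The arithmetic criticism is right: 20.25 is not the SD of these four ages. With the stated mean and whole-year ages the SD would be between 14.38 and 16.74. No change to the plan follows, because the error is confined to one descriptive entry on which nothing in the trial depends. Eligibility, the choice of sample size, the primary and secondary results and the conclusions would all read the same with the correct figure. The printed BDI-II statistics agree with one another, so there is no sign that the slip extends to the primary outcome.

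The bounds assume that n = 4 and the range of 36 to 70 are correct; the narrower ones also assume the mean of 56.25. If the mean were the faulty figure, 20.25 would still be excluded, but only narrowly once rounding of ages is allowed (20.21). If the range were the faulty figure these bounds would no longer apply, yet the consequence would still be limited to the description of the sample.

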### *3.2 Depression Inventory Effects*

Changes in individual's BDI-II score were calculated and recorded in Table 2. The Shapiro-Wilk test yielded data normality among the BDI-II pre-intervention and post-intervention scoring; therefore, the paired student t-test via Statistical Package for the Social Sciences (SPSS) V. 26 was utilized to analyze this data (Table 4 & 5). There was not a statistically significant difference found between pre- and post-intervention scoring ( $p=0.196$ ).

### *3.4 Adverse Effects*

Potential adverse effects were identified at the beginning of this study that could possibly result from exposure to bright light therapy. These effects included eyestrain, headache, nausea,

irritability or agitation, and breach of confidentiality. There was no occurrence of adverse events to disclose for this project.

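### No adverse-effect questioning is described after the 10-minute pretest, so zero events in four participants cannot be shown to cover mania or migraine and does not support a well-tolerated conclusion

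*Combined protocol and SAP*

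**What the plan says.** Section 2.1 gives reasons for its exclusions. Two of them name effects of the light: it excludes "those with bipolar disorder because light therapy may trigger mania" and also excludes patients with "migraines because the bright light could be a trigger".

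Section 3.4 lists the potential adverse effects identified at the start: "These effects included eyestrain, headache, nausea", followed by "irritability or agitation, and breach of confidentiality". It then reports: "There was no occurrence of adverse events to disclose for this project". The Abstract repeats the zero and concludes that the therapy is well tolerated in hospitalized adults with CF or COPD.

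On collection, section 2.3 says that the Mood Disorder Questionnaire "was administered manually from a printed paper survey during the pre-screening process to determine history of bipolar disorder symptomatology". It also describes a 10-minute pretest after consent to look for acute reactions, and routine monitoring by the PI for disruptions to sessions. Disruption information went onto the compliance log. Section 2.4 gives the log's fields as the date, whether therapy was started, at what time, and whether it was interrupted. It adds: "Reason for interruption could be added as a comment on the log, but there was no designated area in which to write it".

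**The concern.** A count of zero adverse events is only as good as the way events were looked for. The document describes a deliberate symptom check before therapy and none during or after it. Mania and migraine, which section 2.1 ties to the light, are not named in the section 3.4 list, and no assessment of manic symptoms is described once exposure begins.

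Participants could switch the lamp off themselves. Section 2.3 gives self-discontinuation as one kind of disruption and leaving the unit for tests, procedures or dialysis as another. Without a set place for the reason, both can end up as the same entry on the log. No tally of reasons is reported.

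This matters because section 2.1 says the main interest is feasibility and acceptability, in support of a larger study. A tolerability statement is therefore one of the main things the study hands on.

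**Working it through.** The documents give no participant-level adverse-event data, so the reported zero cannot be re-derived. The check sets the described sources of safety information side by side and then sizes what a zero in four participants can show.

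**1. Where an adverse effect could have been recorded**

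| Source | Section | When | Described purpose | Adverse-effect question described? |
|---|---|---|---|---|
| Mood Disorder Questionnaire | 2.3 | Pre-screening | Bipolar history | No; it precedes exposure |
| 10-minute pretest | 2.3 | After consent, before the first full session | Acute reactions (eyestrain, headache, nausea, irritability) | Yes, once |
| Daily log | 2.4 | Each day | Date, started, time, interrupted | No; reason only as an optional comment |
| PI monitoring | 2.3 | Routine, frequency not stated | Disruptions, lamp settings | None described |
| PI contact details | 2.3 | Any time | Use if needed | No; depends on someone calling |
| Repeat BDI-II | 2.3, 2.4 | After the intervention | Depressive symptoms | None described |

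Only the pretest is described as a symptom check, and it came before every 30-minute session.

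**2. Exposure behind the zero** (section 3.3)

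- Completed therapy days: 7 + 6 + 2 + 3 = 18.
- Planned: 4 participants × 7 days = 28.
- Delivered: 18/28 = 64%. The other 28 − 18 = 10 days are not broken down by reason. Section 5 cites staffing and off-unit care, without counts.

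**3. What 0 of 4 can exclude, if every event had been found**

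- Two-sided exact 95% interval: the lower limit is 0. The upper limit is 1 − 0.025^(1/4) = 1 − 0.398 = 0.602, or 60.2%.
- One-sided 95% upper bound: 1 − 0.05^(1/4) = 1 − 0.473 = 0.527, or 52.7%.
- For comparison, zero events in the target sample of 30 would give a one-sided bound of 1 − 0.05^(1/30) = 0.095, or 9.5%.

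**4. Chance of seeing at least one event in four participants**, 1 − (1 − p)^4. The per-patient risks p are assumed, because the documents give none.

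| Assumed risk p | Chance of at least one event |
|---|---|
| 5% | 18.5% |
| 10% | 34.4% |
| 20% | 59.0% |
| 30% | 76.0% |

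An effect with a true risk of 10% would more likely than not be missed, even with perfect ascertainment.

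**The case against.** The strongest reply has four parts.

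- The section 3.4 list is introduced as what the effects included, so it is not stated to be exhaustive, and the zero that follows is not limited to it. Read literally, it covers mania and migraine.
- Section 2.1 deals with both risks by exclusion. Bipolar symptomatology was screened for, and section 3.1 shows two candidates excluded for migraine history. Headache and irritability or agitation overlap with migraine and manic symptoms.
- The log was not the only source. There was the pretest, the PI's monitoring, contact details for participants and staff, and a statement in section 2.3 that disruption information was recorded on the log.
- With four participants, sample size limits the zero more than form design does. Better forms would not narrow the interval.

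All of this stands as description. A reader might infer that the zero leaves out mania and migraine, that effects were never asked about, or that mania was not monitored. The documents support none of these. They are silent on what the PI asked at routine visits, and silence shows only that a method is not described.

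The narrower point remains. Exclusion by history does not rule out a first episode, and section 2.3 itself says that bipolar history could not be settled from the chart alone. Overlapping symptoms on a list help little when no later question about them is described. The remaining sources depend on someone volunteering an effect or writing an unprompted comment, and section 5 reports that staff had trouble even starting sessions.

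**Conclusion.** The point holds as one of undescribed ascertainment. After the pretest no systematic adverse-effect question is described, and after pre-screening no assessment of manic symptoms. The reasons for interrupted sessions may not be recoverable from the log. The zero in 4 participants over 18 of 28 planned therapy days therefore cannot be shown to cover mania, migraine or intolerance that ended a session, and it does not support the Abstract's tolerability conclusion. Mania is the stronger example; migraine is weaker because headache is listed.

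The size is an upper 95% limit of 60.2% per patient, before any allowance for missed events. This assumes that the four reported participants were everyone exposed to the lamp and that sections 2.3 and 2.4 describe all safety data collection. If the investigator can document symptom questions at the routine visits, the ascertainment concern shrinks to a reporting gap and the wide interval remains.

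**What to change.** **For the data in hand.** In section 3.4 and the Abstract:

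- State how, when and by whom adverse effects were asked about, and whether new migraine or manic symptoms were assessed. Only the investigator can supply this; the text should not assert that they were not assessed unless that is confirmed.
- Report 0/4 with its exact 95% interval of 0 to 60.2%.
- Replace the well-tolerated conclusion with a statement that no adverse events were noted in four participants.

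**For further use of the design.** In section 2.4:

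- Add a reason field beside the interruption item with three codes: stopped by the participant for symptoms, stopped by the participant for another reason, and off-unit or procedure.
- Have the PI complete a short yes/no checklist at the existing routine visits and with the repeat BDI-II. It should cover eyestrain, headache or migraine, nausea, irritability or agitation, and elevated mood.
- Keep the checklist in the confidential study record. The daily log hangs on the room door, and section 3.4 itself counts breach of confidentiality as a risk. That risk needs no per-session tick.

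**Cost.** Slightly more form work for the PI, a few sentences of reporting, probably more minor effects recorded, and a less favourable tolerability statement.
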